8.5. Pharmacokinetics

- Blood samples will be collected for measurement of serum concentrations of belimumab as specified in the SoA (Section 1.3) and Table 2. Instructions for the collection and handling of biological samples will be provided by the sponsor. The actual date and time (24-hour clock time) of each sample will be recorded.
- Samples collected for analyses of belimumab serum concentrations may also be used to help evaluate safety or efficacy questions arising during or after the study.

Table 2 PK visit days and sample times for study participants

Sampling	Body weight ≥ 50 kg		Body weight ≥ 30 kg to < 50 kg		Body weight ≥ 15 kg to < 30 kg	
	Belimumab 200 mg weekly		Belimumab 200 mg SC every 10 days		Belimumab 200 mg SC every 2 weeks	
	Visit	Day	Visit	Time	Visit	Time
Additional PK ^a	V1 ^a	Screening	V1 ^a	Screening	V1 ^a	Screening
1	V2 ^b	Day1	V2 ^b	Day1	V2 ^b	Day1
2	V3 ^c	Day4 \pm 1	V3 ^c	Day4 \pm 1	V3 ^c	Day4 \pm 1
3	V4 ^{b,d}	Day8 \pm 2	V4 ^{b,d}	Day11 \pm 2	V4 ^{b,d}	Day15 \pm 2
4	V14 ^b	Day78 \pm 1	V10 ^b	Day71 \pm 1	V8 ^b	Day71 \pm 1
5	V15	Day81 \pm 1	V11	Day74 \pm 1	V9	Day74 \pm 1
6	V16	Day85 \pm 2	V12	Day81 \pm 2	V10	Day85 \pm 2

^a. For those participants who don't have IV PK samples in study 213560, 3 additional PK samples will be collected within 4 hours, at 7 days (± 2 days) and 14 days (± 2 days) after last belimumab IV infusion at week 48 of study 213560.

^b. Samples must be taken pre-dose where the dose is administered on a clinic visit day.

If sampling for PK is missed at Visits 3 and Visit4, the impact will be minimized by attempting to reschedule the missing PK sampling to ensure sufficient precision of PK characterization in Chinese paediatric participants:

- ^c. For the scenario that if the sample collection on visit 3 (Day 4 \pm 1 day) was missed, then that PK sample collection should be rescheduled at 3 \pm 1 day after any of the next doses.
- ^d. For the scenario that if the sample collection on visit 4 (Day 8/11/15 \pm 2 day) was missed, the PK sample collection should be rescheduled to when participants take the next dose and the sample must be taken pre-dose.

Further guidance and information on PK sampling and PK reschedule is provided in SRM.

8.6. Genetics

Genetics are not evaluated in this study.

8.7. Biomarkers

Biomarkers are not evaluated in this study.

8.8. Immunogenicity Assessments

Immunogenicity parameters are not evaluated in this study.

8.9. Health Economics OR Medical Resource Utilization and Health Economics

Health economics/medical resource utilization and health economics parameters are not evaluated in this study.

9. STATISTICAL CONSIDERATIONS

9.1. Statistical Hypotheses

The study is designed to descriptively evaluate the PK and safety of belimumab plus standard therapy, and as such no formal statistical hypothesis testing is planned.

9.2. Analysis Sets

- The following populations are defined:

Population	Description
Screened	All participants whose parent/caregiver sign the ICF
Enrolled	All participants assigned treatment.
Intent to Treat (ITT)	All participants assigned treatment who received at least one dose of study treatment.
PK	All participants assigned treatment who received at least one dose of study treatment and for whom at least one post belimumab treatment PK sample was obtained and analyzed.

9.3. Statistical Analyses

9.3.1. General Considerations

No formal hypothesis testing is planned in the study; all analyses are descriptive.

9.3.2. Primary Endpoint(s)/Estimands(s) Analysis

All pharmacokinetic analyses will be performed on the PK Population. Primary PK analysis will be performed after PK sample collection in all participants has been completed. A population PK analysis will be carried out based on dataset combining PK and demographic data collected in this study (217091) and from studies 213560, BEL114055 and 200908. Individual belimumab exposure parameters ($AUC_{ss, 0-\tau}$, $C_{avg,ss}$, $C_{min,ss}$, $C_{max,ss}$) for study 217091 participants will be derived using the population PK model and a statistical summary on these parameters will be performed.

Endpoint	Statistical Analysis Methods
Primary	Endpoints: 
 Belimumab exposure parameters: $AUC_{ss, 0-\tau}$, $C_{avg,ss}$, $C_{min,ss}$, $C_{max,ss}$ Analysis:

Endpoint	Statistical Analysis Methods
	Descriptive statistics(arithmetic mean, standard deviation of the untransformed data, 95% confidence intervals for the arithmetic mean, median, 25th and 75th percentiles, minimum and maximum, geometric mean, standard deviation of the log-transformed data, 95% confidence intervals for geometric means, between subject coefficient of variation (%CVb, if applicable) will be used to summarize the belimumab exposure parameters: $AUC_{ss, 0-t}$, $C_{avg,ss}$, $C_{min,ss}$, $C_{max,ss}$

Belimumab exposure parameters ($AUC_{ss, 0-t}$, $C_{avg,ss}$, $C_{min,ss}$, $C_{max,ss}$) estimated for all subjects of this study will be summarised and reported in the clinical study report (CSR) of this study. The belimumab exposure parameters will be estimated using a population PK approach based on the integrated dataset including the PK and demographic information from study 213560, 217091, 200908, BEL114055, and may also include PK from other relevant studies in adults. The detailed information about the methods, the results e.g. parameter estimation, goodness of fit, etc. will be reported separately in a model report.

Further details on the population PK analysis will be discussed in the population PK reporting and analysis plan.

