- Participants ≥ 50 kg body weight will receive belimumab 200 mg SC weekly.
- Participants ≥ 30 kg to < 50 kg body weight will receive belimumab 200 mg SC every 10 days.

- Participants ≥ 15 kg to < 30 kg body weight will receive belimumab 200 mg SC every 2 weeks.

The dosing frequency fixed according the baseline body weight.

Data Monitoring/ Other Committee: No

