2.2.3. Pharmacokinetics of IV Belimumab

The pharmacokinetics of IV belimumab (dose ranging from 1 to 20 mg/kg) has been extensively studied in adults with SLE studies (Phase 1, Phase 2, and Phase 3). The PK has been studied in a smaller paediatric population (study BEL114055) and in Chinese adults (study BEL113750, 200909 and 209629). Population PK analyses have been conducted in both adults (Report No. HGS1006-POPPK) and paediatrics (BEL114055 POPPK). The results showed belimumab PK to be body-weight-dependent, dose-proportional and time-invariant after IV administration, similar to many monoclonal antibodies targeting soluble ligands. Geometric mean values of steady-state maximum concentration (C_{max}), minimum concentration (C_{min}), average concentration (C_{avg}), and area under the curve (AUC) were estimated to be 315 µg/mL, 50 µg/mL, 108 µg/mL, and 3012 day · µg/mL respectively in the overall paediatric population; 305 µg/mL, 42 µg/mL, 92 µg/mL, and 2569 day · µg/mL in the 5-11-year-old group, and 317 µg/mL, 52 µg/mL, 112 µg/mL, and 3126 day · µg/mL in the 12-17-year-old group compared to 311 µg/mL, 46 µg/mL, 100 µg/mL, and 2811 day · µg/mL in adults, indicating no great difference exists in steady-state exposure between paediatric and adult populations. The slightly decreased exposure in younger participants was expected due to the allometric effect of lower body weight combined with weight proportional dosing. Because of body weight difference between Asian and Caucasian adult participants, there is small difference in exposure of belimumab when the same weight proportional dosing regimens are given. However, no clinically relevant difference in efficacy has been observed.

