3. OBJECTIVES AND ENDPOINTS AND/OR ESTIMANDS

Objectives	Endpoints
Primary - Pharmacokinetics	

 To characterize belimumab exposure following belimumab 200 mg SC in Chinese paediatric systemic lupus erythematosus (SLE) participants who have previously been treated with IV belimumab 	
 Exposure parameters; $AUC_{ss, 0-T}$, $C_{avg,ss}$, $C_{min,ss}$, $C_{max,ss}$,
Secondary - Safety	

 To evaluate the safety and tolerability of belimumab 200mg SC in paediatric Participants with SLE who have previously been treated with IV belimumab 	
 Occurrence of adverse events, serious adverse events and adverse events of special interest through Week 12.

$AUC_{ss, 0-T}$ = Area under the curve at steady-state to the end of the dosing period, $C_{avg, ss}$ = Average serum concentration at steady state, $C_{min, ss}$ = Minimum serum concentrations at steady state, $C_{max, ss}$ = Maximum serum concentrations during the dosing interval at steady state

Primary estimands

For estimand strategy in primary endpoint. The estimand is described by the following attributes:

Population	Chinese paediatric participants 5-17 years of age with SLE who have previously been treated with IV belimumab
Treatment	
 Repeat doses of 200mg belimumab administered SC over 12 weeks on a background of standard of care therapy
Endpoints	
 Exposure parameters; $AUC_{ss, 0-T}$, $C_{avg,ss}$, $C_{min,ss}$, $C_{max,ss}$,
Summary Measure	
 Geometric mean
Intercurrent events and strategies	
The anticipated key intercurrent events and corresponding strategies are:
 
 Discontinuation of study medication: while-on-treatment strategy. The PK data after study medication discontinuation (except for PK data from EW visit) will not be used in analysis. Specially, to maximize PK data to support the estimation of

	
exposure parameters, the PK data from EW visit will be used in analysis.
 
 • Interruption of study medication: treatment policy strategy. The PK data after interruption of study medication will be used in analysis. • Using of prohibited medications or therapies: while-on-treatment strategy. Only the PK data before initiation of prohibited medications or therapies will be used in analysis.
--	---

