4.3. Justification for Dose

The dose and dosing regimens selected for SC administration in this study are based on calculations intended to achieve a similar average exposure as observed with the weekly 200 mg SC dosing regimen in adult Participants with SLE, estimated from a population PK analysis of SC study data in adults, where the estimated bioavailability (F) was 74.2% without inter-individual variability (IIV) and clearance (CL) was 204 mL/day with 30.2% (CV%) IIV [GSK Document Number [2016N291332_00](#)]. For a fixed belimumab dose (e.g. 200 mg SC), the exposure increases as body weight decreases, as observed in adults and supported by the population PK model developed from the paediatric IV study BEL114055. To accommodate children between the ages of 5 to 17 years, specifically to ensure that participants with lower body weight are not over-exposed, 3 belimumab SC dose groups were proposed and defined by body weight for study 200908 in non-Chinese paediatric participants. Paediatric participants weighing 50 kg or more will receive 200 mg belimumab once a week (QW), as per the recommended dosing regimen in adults. Paediatric participants who weigh between 30 to 50 kg will receive as 200 mg belimumab administered once every ten days (Q10d). Paediatric participants weighing less than 30 kg will receive 200 mg belimumab once every two weeks (Q2W). Belimumab exposure ($C_{ss, avg}$) in paediatrics is predicted to be very similar across the three dose groups, as shown in the exposures projected in overseas paediatrics ([Figure 1](#)). According to the recommended dose regimen, a higher peak-trough ratio is expected in participants with lower body weight; however, safety is not considered as an issue because even greater PK fluctuation was observed in the participants following 10 mg/kg every four weeks (Q4W) IV belimumab. The effects of body weight on belimumab PK are expected to be the same in overseas participants as in Chinese participants. Therefore, the proposed three-tier dosing regimen used in study 200908, with Q2W dosing for participants <30 kg, Q10d dosing for participants between 30 and <50 kg, and QW dosing for participants ≥ 50 kg is considered appropriate for use in this study in Chinese paediatric participants.

Figure 1 Average serum concentrations at steady state versus body weight projected in overseas paediatrics

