Pediatric predictions for the median (solid black line), inter-quartile range (dark grey shaded region) and 90% prediction interval (light grey shaded area) are compared with the post-hoc adult estimates (blue points) and the population adult estimate (broken red, 104 ug/mL). The median pediatric concentrations at the 30 mg and 50 mg body weight thresholds are shown (red diamonds 88 and 123 ug/mL at 30 kg, 90 and 129 ug/mL at 50 kg).

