6.5. Dose Modification

No dose modifications of belimumab are allowed. Dosing frequency are fixed according the baseline body weight.

Dosing cohort	Dosing frequency
BW \geq 50 kg at baseline	Every week
BW \geq 30 kg and <50 kg at baseline	Every 10 days
BW \geq 15 kg and <30 kg at baseline	Every 2 weeks

BW= Body weight

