9.5. Sample Size Determination

There are no formal calculations of power for this study. The sample size justification for study 217091 is based on the precision in the estimate of the geometric mean of $C_{avg,ss}$, over all study participants. The coefficient of variation (CV) for between-subject variability in $C_{avg,ss}$ was approximated to 35.5%, equal to the variability evaluated in overseas children receiving belimumab IV in study BEL114054 [Dimelow, 2020], on the

basis that bioavailability for SC dosing is similar in all subjects and does not significantly increase variability in exposure.

$C_{avg,ss}$ is expected to be log-normally distributed and the 95% confidence interval (CI) relative to the geometric mean is given by $\exp(\pm t_{97.5, N-1} \times sd / \sqrt{N})$, where $t_{97.5, N-1}$ is the 97.5th percentile of the t-distribution with N-1 degrees of freedom, sd is the standard deviation in the logarithm of $C_{avg,ss}$ equal to 0.345 for 35.5% CV, and N is the number of subjects.

For N of 14, the 95% confidence interval in $C_{avg,ss}$ relative to the geometric mean is 82% to 122%. The 95% CI therefore lies within 22% of the point estimate for C_{avg} and this level of precision is considered adequate to characterise belimumab exposure in Chinese children receiving belimumab SC.

Considering the withdrawal rate in the previous and ongoing Benlysta paediatric studies in overseas and China, the withdrawal rate in the current study is estimated to be 20%. To account for a 20% withdrawal rate, the total sample size is 17.

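### Protocol 9.3.2 and the primary estimand give one unstratified summary of AUCss,0-τ although τ is 7, 10 or 14 days by weight tier, and the supplied text names no by-cohort PK summary

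*Protocol*

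**What the plan says.** Protocol section 3 names four primary exposure parameters: AUCss,0-τ, Cavg,ss, Cmin,ss and Cmax,ss. It defines the first as "Area under the curve at steady-state to the end of the dosing period". The primary estimand has a single population, and its summary measure is the geometric mean.

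Protocol 9.3.2 gives one list of descriptive statistics for all four parameters, including the geometric mean with its 95% CI and, where applicable, %CVb. It says that the parameters "estimated for all subjects of this study will be summarised and reported in the clinical study report (CSR) of this study". No weight tier or dosing cohort is mentioned.

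The interval between 200 mg doses is 7 days at 50 kg or more, 10 days from 30 kg to below 50 kg, and 14 days from 15 kg to below 30 kg. Protocol 6.5 adds: "Dosing frequency are fixed according the baseline body weight".

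The SAP does not fill the gap. SAP 4.2 sends the primary endpoints to a separate reporting and analysis plan (RAP) and adds only a listing of concentrations. SAP 4.4.1 lists the three weight tiers as subgroups without naming an endpoint. The displays that the SAP ties to a weight split are extent of exposure (4.3.1), adverse events (4.3.2), withdrawals by visit (6.1.1) and baseline data (6.1.2). None is a PK parameter.

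**The concern.** An area under the curve over 7 days and one over 14 days are not the same quantity. Protocol 4.3 chose the intervals so that average exposure "in paediatrics is predicted to be very similar across the three dose groups". If that works as intended, AUCss,0-τ has to differ between tiers, because it is average concentration multiplied by interval length. A single geometric mean over all children would then partly describe how many fell into each tier.

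What is at stake is the reading of one of four primary figures in the study report. Set beside Cavg,ss, a pooled AUC would show a level that has no regimen attached to it and a larger %CVb. A reader could take that %CVb for greater variability in average exposure.

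**Working it through.** **Inputs.** F = 74.2% and CL = 204 mL/day (protocol 4.3, adult SC model). Adult Cavg,ss 104 µg/mL and the projected paediatric medians "88 and 123 ug/mL at 30 kg, 90 and 129 ug/mL at 50 kg" (Figure 1 legend). CV of Cavg,ss 35.5%, log-SD 0.345, N = 14 and total 17 (protocol 9.5). The documents give no tier mix, so every mix below is an assumption. τ is read as the dosing interval.

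**1. The plan's own precision figure.** exp(±t(0.975, 13) × 0.345 / √14) = exp(±2.160 × 0.345 / 3.742) = 82% to 122%. This reproduces protocol 9.5.

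**2. What AUCss,0-τ measures.** At steady state AUCss,0-τ = F × dose / CL = Cavg,ss × τ.
- Adult model: 0.742 × 200 mg / 204 mL/day = 727 day·µg/mL. Divided by 7 this is 103.9, matching the stated 104.
- Figure 1 at 30 kg, taking the lower value as the longer interval: 88 × 14 = 1,232 and 123 × 10 = 1,230.
- Figure 1 at 50 kg: 90 × 10 = 900 and 129 × 7 = 903.

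At a given weight, changing the interval moves Cavg,ss by about 40% (123/88 = 1.40; 129/90 = 1.43) and leaves AUCss,0-τ where it was. Between weights it does change: 1,232 at 30 kg against 900 at 50 kg, about 37% higher, because clearance falls with weight.

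**3. Tier values at equal average exposure.** With Cavg,ss = 104: 104 × 7 = 728, 104 × 10 = 1,040 and 104 × 14 = 1,456 day·µg/mL, a ratio of 1 : 1.43 : 2.

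**4. Pooled summary for 17 children.** Geometric mean = 104 × exp(mean of ln τ). Total log-SD = √(0.345² + SD(ln τ)²), which assumes that τ is independent of Cavg,ss. CV = √(exp(SD²) − 1).

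| Assumed mix QW/Q10d/Q2W | Geometric mean | SD(ln τ) | Total log-SD | CV |
|---|---|---|---|---|
| 12/4/1 | 825 | 0.207 | 0.402 | 41.9% |
| 9/6/2 | 896 | 0.242 | 0.421 | 44.1% |
| 6/6/5 | 1,012 | 0.278 | 0.443 | 46.6% |

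The geometric mean moves by 23% (1,012/825 = 1.23) with Cavg,ss held the same in every child.

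**5. Interval width at N = 14.** Using the formula of step 1 with the total log-SD: mix 10/3/1 (0.406) gives about 79–126%, and mix 5/5/4 (0.443) about 77–129%, against 82–122% for Cavg,ss.

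**The case against.** Five points can be made for the plan as it stands.

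- **The extra spread is real.** A reader might infer that part of the pooled %CVb is merely an artefact of mixing interval lengths. The documents do not support that. Step 2 shows that at a given weight AUCss,0-τ does not change with τ. The spread between tiers is weight-related variation in clearance, which the intervals were set to offset in Cavg,ss. This stands: a larger %CVb for AUC would be correct as variability in exposure per dose. It would be wrong only if read as variability in average exposure.
- **Pooling is inferred.** Protocol 9.3.2 never says that there will be only one summary, and its wording may simply separate this study's participants from the other studies in the model dataset. This stands in part. An unstratified list and a single estimand population still make a pooled summary the plain reading.
- **The split may exist elsewhere.** The PK RAP was not supplied, and SAP 4.4.1 is not confined to safety. This stands: the text supports that the split is not specified in what was supplied, not that it will be omitted.
- **Cavg,ss already does the job.** It is a primary parameter, and protocol 9.5 says "The sample size justification for study 217091 is based on the precision in the estimate of the geometric mean of" Cavg,ss. This also stands, and limits the consequence to presentation.
- **The sizes are assumption-driven.** The mixes are invented. Independence of τ and Cavg,ss is a simplification too, since Figure 1 has Cavg,ss falling from 123 to 90 µg/mL across the 10-day tier.

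It is also tempting to set a paediatric 10-day AUC against the adult weekly 728 and call the gap an effect of interval length. Figure 1 does not bear that out: at 50 kg the paediatric weekly and 10-day values are practically equal (903 and 900).

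**Conclusion.** The point holds as a low-cost improvement to reporting. As written, the primary summary of AUCss,0-τ combines exposure per dose across three regimens, and its geometric mean depends on the enrolled weight mix. The range is about 825 to 1,012 day·µg/mL at Cavg,ss 104 under the assumed mixes of 17. The pooled CV would be about 42–47% against 35.5%, if τ is independent of Cavg,ss; any association between them would change that figure.

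A reader might go further and infer that the sample size, the dosing regimen or the validity of the primary analysis is in doubt. The documents do not support this. The sample size rests on Cavg,ss, which pooling over tiers does not distort. The regimen is to be chosen by simulation from the updated population PK model (protocol 2.1). All analyses are descriptive (protocol 9.3.1). Nor is there a case for removing AUCss,0-τ from the primary parameters. Confidence is medium, because the RAP that governs the primary endpoints was not available.

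**What to change.** In the PK RAP, and in protocol 9.3.2 at the next amendment, if not already there:

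- Summarise AUCss,0-τ by dosing cohort (QW, Q10d, Q2W), beside Cavg,ss, Cmin,ss and Cmax,ss for the same cohorts.
- Name Cavg,ss as the pooled exposure measure.
- Keep any pooled AUCss,0-τ with a footnote that it combines 7-, 10- and 14-day intervals.
- State in SAP 4.4.1 that the weight subgroups apply to the PK parameters.

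The cost is a few sentences and some extra table columns, with no new data. The protocol wording can wait for the next amendment, since protocol 10.1.1 requires ethics approval of any amendment.

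The downside is imprecision within cohorts. From exp(±t(0.975, n − 1) × 0.345 / √n), six children give about 70–144% and three give 42–236%. The by-cohort figures are descriptive only and cannot reliably show or exclude differences between tiers.

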9.3.3. Secondary Endpoint Analysis

All safety analyses will be performed on the ITT population.

Endpoint	Statistical Analysis Methods
Secondary (Safety)	
Endpoints: Occurrence of adverse events, serious adverse events and adverse events of special interest through Week12.
 
Analysis: Descriptive statistics (frequency and percentage) will be used to summarize AEs, SAEs, and AESIs. The frequency of AEs will be tabulated by MedDRA SOC and preferred term (PT).

9.4. Interim Analysis

No formal interim analyses are planned.

9.5. Sample Size Determination

There are no formal calculations of power for this study. The sample size justification for study 217091 is based on the precision in the estimate of the geometric mean of $C_{avg,ss}$, over all study participants. The coefficient of variation (CV) for between-subject variability in $C_{avg,ss}$ was approximated to 35.5%, equal to the variability evaluated in overseas children receiving belimumab IV in study BEL114054 [Dimelow, 2020], on the

basis that bioavailability for SC dosing is similar in all subjects and does not significantly increase variability in exposure.

$C_{avg,ss}$ is expected to be log-normally distributed and the 95% confidence interval (CI) relative to the geometric mean is given by $\exp(\pm t_{97.5, N-1} \times sd / \sqrt{N})$, where $t_{97.5, N-1}$ is the 97.5th percentile of the t-distribution with N-1 degrees of freedom, sd is the standard deviation in the logarithm of $C_{avg,ss}$ equal to 0.345 for 35.5% CV, and N is the number of subjects.

For N of 14, the 95% confidence interval in $C_{avg,ss}$ relative to the geometric mean is 82% to 122%. The 95% CI therefore lies within 22% of the point estimate for C_{avg} and this level of precision is considered adequate to characterise belimumab exposure in Chinese children receiving belimumab SC.

Considering the withdrawal rate in the previous and ongoing Benlysta paediatric studies in overseas and China, the withdrawal rate in the current study is estimated to be 20%. To account for a 20% withdrawal rate, the total sample size is 17.

